### **Thrombosis With Thrombocytopenia Syndrome**

In the context of worldwide vaccination following Emergency Use Authorization (EUA), conditional licensure, or approval by health authorities, thrombosis in combination with thrombocytopenia (thrombosis with thrombocytopenia syndrome [TTS]), in some cases accompanied by internal bleeding, has been observed following vaccination with the Janssen COVID-19 (Ad26.COVS.2) vaccine. As of 31 August 2021, out of 33,584,049 doses of

Ad26.COV2.S administered post-marketing, the following spontaneous reported/solicited reports of probable TTS cases were identified. a

- A total of 104 post-marketing events that met the Brighton TTS Case Definition Criteria Level 1 to 3 ([Brighton Collaboration 2021](#)). This corresponds to a reporting ratio of 3.1 per million doses overall.
- A total of 67 post-marketing events that met the CDC TTS Case Definition Criteria Tier 1 to 2 ([Shimabukuro 2021](#)). This corresponds to a reporting ratio 2 per million doses overall.

Reports include severe cases of venous thrombosis at unusual sites such as cerebral venous sinus thrombosis (CVST), splanchnic vein thrombosis and arterial thrombosis, in combination with thrombocytopenia. Venous thrombosis cases have also been reported at more common sites, eg, in the lower extremities. The onset of associated symptoms has usually been 1 to 4 weeks, but sometimes even later following vaccination. TTS cases have been reported mostly in women under 60 years of age although some cases of TTS have also been reported in men and in individuals older than 60 years of age. Thrombosis in combination with thrombocytopenia has been fatal in some cases. The exact pathophysiology of TTS is unclear. This event has not been observed to date with any other Janssen Ad26-based vaccines. Participants should be instructed to seek immediate medical attention if they develop symptoms such as shortness of breath, chest pain, leg pain or leg swelling, persistent abdominal pain, severe or persistent headaches, blurred vision, skin bruising and/or petechiae beyond the site of vaccination, changes in mental status or the occurrence of seizures.

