#### **Adverse Events**

The verbatim terms used in the eCRF by investigators to identify AEs will be coded using the Medical Dictionary for Regulatory Activities (MedDRA). All reported AEs with onset during the active phase (ie, AEs occurring after vaccination up to 28 days post-vaccination) or AEs present before the active phase but worsening during the active phase, and all SAEs and AESIs will be included in the analysis. For each AE, the percentage of participants who experience at least 1 occurrence of the given event will be summarized by intervention group.

Summaries, listings, datasets, or participant narratives may be provided, as appropriate, for those participants who die, who discontinue intervention due to an AE, or who experience a severe AE, an AESI, an SAE or a COVID-19 infection.

Solicited local (at injection site) and systemic AEs will be summarized descriptively. The number and percentages of participants with at least one solicited local (at injection site) or systemic adverse event will be presented. The frequencies by vaccine group as well as frequencies according to severity and duration will be described for solicited AEs. Frequencies of unsolicited AEs, separately for all and vaccination-related only, will be presented by System Organ Class and preferred term, while those of solicited AEs will be presented only by preferred term.

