## **9.5. Planned Analyses**

The following analyses are planned:

- Primary analysis: 28 days post-vaccination safety and immunogenicity analysis. This analysis will be performed when all participants in Cohort 1 and Cohort 2 have completed their 28-day post-vaccination visit. Data from corresponding arms from the 2 cohorts will be combined. The goal of this analysis will be to select the vaccine formulation to be used in Cohort 3.
- Interim analyses:
  - 6-month post-vaccination safety and immunogenicity analysis for Cohorts 1 and 2. Available safety and immunogenicity data of all participants in Cohort 1 and Cohort 2 up to the Day 185 follow-up visit post-vaccination will be included in the analysis. This analysis may include immunogenicity data available from additional timepoints.
  - 1-year post-vaccination immunogenicity analysis for Cohorts 1 and 2. Immunogenicity data of all participants in Cohort 1 and Cohort 2 up to (and including) the 1-year follow-up visit post-vaccination will be included in the analysis.
  - 28 days post-vaccination safety and immunogenicity analysis for Cohort 3. This analysis will be performed when all participants in Cohort 3 have completed their 28-day post-vaccination visit.
  - 28 days post-vaccination safety and immunogenicity analysis for Cohort 4. This analysis will be performed when all participants in Cohort 4 have completed their 28-day post-vaccination visit.
  - 6-month post first vaccination safety and immunogenicity analysis for Cohorts 3 and 4. This interim analysis will include all safety and immunogenicity data from all participants in Cohorts 3 and 4, collected up to (and including) the 6-months follow-up visit post Day 1 vaccination.

28 days post revaccination safety and immunogenicity analysis for Cohorts 3 and 4. This interim analysis will include all safety and immunogenicity data from all participants in Cohorts 3 and 4, collected up to (and including) the 28-day post-revaccination visit.

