### 5.3. Primary Endpoint(s) Analysis

#### 5.3.1. Definition of Endpoints

For cohort 1 to 3 the primary safety endpoints are defined as:

- Serious adverse events (SAEs) and adverse events of special interest (AESIs) from first dose administration until 6 months after vaccination
- Solicited local and systemic adverse events (AEs) for 7 days after vaccine administration
- Unsolicited AEs from the time of vaccine administration through the following 28 days

In addition, for cohorts 1 and 2, and cohort 4 the primary immunogenicity endpoint is defined as RSV neutralization antibody titers.

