**Definition of intervals:**

Dose	Interval	From	to
Post-vaccination 1	0-28 days post dose	Date time of the 1 st vaccination	Min of: 
 
23:59 at the date of last contact (for discontinuations)
 
23:59 at date of DB cut-off for interim analyses
 
Maximum(Date of Vaccination 1 + 28 days at 23:59, date of scheduled visit 4 weeks after 1st vaccination at 23:59)
 

	29-56 days post dose	One minute after the end of the interval 0-28 days post dose	Min of: 
 
23:59 at date of last contact (for discontinuations)
 
23:59 at date of DB cut-off for interim analyses
 
Date of Vaccination 1 + 56 days at 23:59
 

	57 days - 6 months post-dose	One minute after the end of the interval 29-56 days post dose	Min of: 
 
23:59 at date of last contact (for discontinuations)
 
23:59 at date of DB cut-off for interim analyses
 
Maximum of (Date of Vaccination 1 + 183 days at 23:59, date of scheduled visit 183 days post 1st vaccination at 23:59)
 

	>6 months post-dose	One minute after the end of the interval 57 days - 6 months post-dose	Min of: 
 
23:59 at the date of last contact (for discontinuations)
 
23:59 at the date of DB cut-off for interim analyses
 

			
 
1 min prior to date time of vaccination 2
 

Post-vaccination 2	0-28 days post dose	Date time of the 2nd vaccination	Min of: 
 
23:59 at the date of last contact (for discontinuations)
 
23:59 at date of DB cut-off for interim analyses
 
Maximum(Date of Vaccination 2 + 28 days at 23:59, date of scheduled visit 4 weeks after 2nd vaccination at 23:59)
 

	29-56 days post dose	One minute after the end of the interval 0-28 days post dose	Min of: 
 
23:59 at date of last contact (for discontinuations)
 
23:59 at date of DB cut-off for interim analyses
 
Date of Vaccination 2 + 56 days at 23:59
 

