## **5.9. Planned Analyses**

The following analyses are planned:

- Primary analysis: 28 days post-vaccination safety and immunogenicity analysis up to D15 for humoral antibodies. This analysis will be performed when all participants in Cohort 1 and Cohort 2 have completed their 28-day post-vaccination visit. For primary analysis humoral immunogenicity will include baseline and Day 15 data, while safety analysis will be included the data up to Day 29 visit. Data from corresponding arms from the two cohorts will be combined. The goal of this analysis will be to select the vaccine formulation to be used in Cohort 3.

- Interim analyses:
  - 84 days post-vaccination immunogenicity analysis for Cohorts 1 and 2. Available immunogenicity data of all participants in Cohort 1 and Cohort 2 up to the Day 85 will be included in the analysis. 6-month post-vaccination safety and immunogenicity analysis for Cohorts 1 and 2. Available safety and immunogenicity data of all participants in Cohort 1 and Cohort 2 up to the Day 185 follow-up visit post-vaccination will be included in the analysis. This analysis may include immunogenicity data available from additional timepoints.
  - 1-year post-vaccination immunogenicity analysis for Cohorts 1 and 2. Immunogenicity data of all participants in Cohort 1 and Cohort 2 up to (and including) the 1-year follow-up visit post-vaccination will be included in the analysis.
  - 28 days post-vaccination safety and immunogenicity analysis for Cohort 3. This analysis will be performed when all participants in Cohort 3 have completed their 28-day post-vaccination visit.
  - 28 days post-vaccination safety and immunogenicity analysis for Cohort 4. This analysis will be performed when all participants in Cohort 4 have completed their 28-day post-vaccination visit.
  - 6-month post first vaccination safety and immunogenicity analysis for Cohorts 3 and 4. This interim analysis will include all safety and immunogenicity data from all participants in Cohorts 3 and 4, collected up to (and including) the 6-months follow-up visit post Day 1 vaccination.
  - 28 days post revaccination safety and immunogenicity analysis for Cohorts 3 and 4. This interim analysis will include all safety and immunogenicity data from all participants in Cohorts 3 and 4, collected up to (and including) the 28-day post-revaccination visit.

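### SAP 5.9 limits safety in the formulation-selection analysis to the Day 29 visit, which conflicts with other SAP and protocol text that carries SAEs and AESIs to the database cut-off

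*SAP*

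**What the plan says.** **SAP 5.9, primary analysis.** On timing: "This analysis will be performed when all participants in Cohort 1 and Cohort 2 have completed their 28-day post-vaccination visit". On purpose: "The goal of this analysis will be to select the vaccine formulation to be used in Cohort 3". On content, humoral data stop at Day 15, "while safety analysis will be included the data up to Day 29 visit". The 28-day analyses of Cohorts 3 and 4 in the same section carry no such sentence.

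**Protocol 9.5** names the same analysis "Primary analysis: 28 days post-vaccination safety and immunogenicity analysis" and excludes no later data.

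**Text pointing the other way:**
- SAP 5.3.1 defines a primary safety endpoint as "Serious adverse events (SAEs) and adverse events of special interest (AESIs) from first dose administration until 6 months after vaccination".
- SAP 5.3.2 admits all SAEs, and potential AESIs and AESIs to 6 months, and reports safety by phase and over the whole study period.
- SAP Table 3 (5.1.2) has a Follow-up 1 phase after the 28-day period. For any analysis before the final one, it runs to the database cut-off at the latest.
- The interval table in SAP 5.3.2.3 has 29-56 day and 57 day-6 month AESI intervals, with one limit being "23:59 at date of DB cut-off for interim analyses".
- Protocol 9.4.4, after describing the 28-day active phase, adds: "and all SAEs and AESIs will be included in the analysis".
- Protocol 4.1 rests the choice of composition on whatever safety and immunogenicity results are available when the primary analysis is done.

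SAP Appendix 2, which lists changes from the protocol-planned analyses, mentions only the grading of laboratory data.

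**The concern.** The primary analysis is the point at which the sponsor is unblinded for Cohorts 1 and 2 (protocol 6.3) and chooses among component combinations. These differ in RSV-A and RSV-B components, protein dose and total Ad26 content, from none in Arm 2 to 2×10^11 vp in Arm 9. Protocol 4.3 says that Ad26 up to that level is tested here for the first time and will be watched closely.

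The protocol's background section says of TTS: "The onset of associated symptoms has usually been 1 to 4 weeks, but sometimes even later following vaccination". A limit at the Day 29 visit sits at the end of the usual window and cuts off the later part. A programmer could reasonably treat the sentence in 5.9 as the specific rule that overrides the general ones. A thrombotic event or thrombocytopenia at Day 40, already reported, would then be missing from the by-arm tables that inform the choice. The 6-month analysis would show it, but no passage ties the start of Cohort 3 to that analysis.

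**Working it through.** **1. Which rule governs?**

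| Text | Specific to the primary analysis? | SAE/AESI data admitted |
|---|---|---|
| SAP 5.9 | Yes | To the Day 29 visit |
| SAP 5.3.2 | No | All SAEs; AESIs and potential AESIs to 6 months |
| SAP Table 3 | Covers it (any analysis before the final) | To database cut-off |
| SAP interval table | Uncertain: says interim analyses, which 5.9 lists apart from the primary | To database cut-off |
| Protocol 9.4.4 | No | All SAEs and AESIs |
| Protocol 4.1 | Yes, for the decision | Results available at that time |

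No text sets an order of precedence.

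**2. Does later follow-up exist at the trigger?** Inputs are from protocol 4.1. Each Cohort 1 group has a 24-hour sentinel pause and then a review seven days after vaccination before the next group starts. Cohort 2 waits for Day 8 data on all of Cohort 1. Take the shortest calendar: no accrual or review time, with the seven days counted from the last vaccination in the group. Each group then takes 1 + 7 = 8 days.

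Non-sentinel participants are vaccinated on calendar days 1, 9, 17 and 25. Cohort 2 starts on day 4 × 8 = 32. If Cohort 2 enrolled in a single day, its 28-day visits fall on day 32 + 28 = 60.

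| Group (N) | Days since vaccination at day 60 | Days beyond Day 29 |
|---|---|---|
| 1 (18) | 60 − 1 = 59 | 59 − 28 = 31 |
| 2 (66) | 60 − 9 = 51 | 23 |
| 3 (30) | 60 − 17 = 43 | 15 |
| 4 (18) | 60 − 25 = 35 | 7 |

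Sentinels have one day more. Any real accrual or review time lengthens these figures. They apply to participants still in follow-up and are counted from Day 29 itself. The visit window is +7 days, so a Group 4 participant seen at the end of it has 35 − 35 = 0 days beyond the visit on this minimum calendar.

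**3. Cohort 2.** Enrolment length E is not given. Assuming uniform enrolment, mean elapsed time beyond Day 29 at the trigger is E/2: 0, 14, 28 or 42 days for E = 0, 4, 8 or 12 weeks. Each Cohort 1 figure above rises by E.

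**4. How much could the later window matter?** The plan gives no figure for this. The nearest is protocol Table 15: with N = 60 (one arm, Cohorts 1 and 2) and a true rate of 1%, 1 − 0.99^60 = 45.3%, which reproduces. Take 1% as the 6-month risk and let s be the share of onsets by Day 29. The chance of seeing at least one event by Day 29 is 1 − (1 − 0.01s)^60:
- onsets spread evenly, s = 28/182 = 0.154: 8.8%
- s = 0.8: 38.2%
- s = 0.9: 41.9%

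The value at the actual cut-off lies between these figures and 45.3%. The shortfall is small for an event with mostly early onset and large for one spread over 6 months. The value of s is an assumption throughout.

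**The case against.** **The stronger reading.** A reader might infer that late SAEs and AESIs are definitely excluded from the choice of formulation. The documents do not support that. SAP 5.3.2 and Table 3 would bring such events in, and protocol 4.1 lets the sponsor use all available results. The 5.9 sentence may be meant only to contrast Day 29 safety with Day 15 humoral data. The defect is an unresolved conflict, not a decided exclusion.

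**Person-time.** A reader might also turn the elapsed days into a share of observed safety data thrown away. That is not supported either. The Cohort 2 part rests on assumed enrolment, and Cohorts 1 and 2 have no scheduled visit between Day 29 and Day 85. Events in that gap surface only if the site learns of them.

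**A common window is legitimate.** It equalises follow-up across staggered groups. On the minimum calendar Arm 9, with the highest total Ad26 content, has the least later follow-up (7 days against 31 for Arm 1a), so raw later counts would be confounded with arm. This stands and shapes the fix.

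**Other safety routes.** SAEs and potential AESIs reach the sponsor within 24 hours (protocol 8.3.1, 8.3.6). The pausing rules (6.9) apply to SAEs and AESIs without the four-week limit set for other AEs. A confirmed TTS case judged related would pause vaccination, so it would not go unnoticed. These routes do not give a by-arm table, however. The DRC looks at blinded data first, and the AESI part of pausing rule 2 covers only confirmed TTS judged related. An isolated late thrombosis judged unrelated would not meet that rule.

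**Conclusion.** The point holds as an internal conflict on what safety data the selection analysis contains. SAP 5.9 says one thing; SAP 5.3.2, SAP Table 3, the interval table, protocol 9.4.4 and protocol 4.1 say another. The limit is not declared in SAP Appendix 2. The consequence is conditional: if 5.9 is applied as written, reported SAEs and potential or confirmed AESIs with onset after the Day 29 visit drop out of the unblinded by-arm tables.

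That later follow-up exists is close to certain: at least about 7 to 31 days beyond Day 29 in Cohort 1, subject to the visit-window caveat for Group 4. Its extent in Cohort 2 is unknown, and so is whether any event falls in it. The protocol's own statement that TTS usually starts within 1 to 4 weeks means that only a minority of TTS onsets would be expected there. The conflict is worth settling before Cohorts 1 and 2 are unblinded, because it costs little and bears on the decision that fixes the product for Cohorts 3 and 4.

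**What to change.** Reconcile the passages in SAP 5.9, before sponsor unblinding for the primary analysis, and record the rule in Appendix 2 if it departs from the protocol:

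1. Keep the Day 29 window for solicited and non-serious unsolicited AEs, and as the like-for-like comparison between arms.
2. State that all SAEs, AESIs, potential AESIs, deaths and AEs leading to discontinuation reported up to the database cut-off are also tabulated by arm.
3. Use the existing 0-28 day, 29-56 day and 57 day-6 month intervals, and show for each arm the number of participants who have reached each one.
4. Say that the cut-off rule in the interval table covers the primary analysis as well as the interim analyses.

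**Cost.** A few sentences. The events are already collected and reported within 24 hours. The interval tables are specified for AESIs, so extending them to SAEs, deaths and discontinuations is a small programming addition. The downside is that follow-up after Day 29 is unequal across the staggered arms and ascertainment between scheduled visits is incomplete. Some potential AESIs may also still await committee review. The later counts must be read with exposure shown and should supplement the Day 29 comparison, not replace it.

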**5.9.1. Data Review Committee (DRC)**

An internal DRC will be established to evaluate safety and reactogenicity data, including interim safety and reactogenicity data of Cohort 1, to ensure the continuing safety of the participants enrolled in this study. The DRC will review blinded data but may request unblinded data if deemed necessary. Ad-hoc meetings will be convened in case any of the pre-specified study vaccination pausing rules are met. This committee will consist of at least one medical expert in the relevant therapeutic area and at least one statistician; committee membership responsibilities, authorities, and procedures will be documented in its charter. After the review, the DRC will make recommendations regarding the continuation of the study.

## 6. SUPPORTING DOCUMENTATION

### 6.1. Appendix 1 List of Abbreviations

ADA	anti-drug antibody
ADaM	Analysis Data Model
AE	adverse event
ANCOVA	analysis of covariance
ATC	anatomic and therapeutic class
Analysis Data Model	Analysis Data Model
BMI	body mass index
CI	confidence interval
CRF	case report form
CSR	Clinical Study Report
CTCAE	Common Terminology Criteria for Adverse Events
DMC	Data Monitoring Committee
DPS	Data Presentation Specifications
ELISA	enzyme-linked immunosorbent assay
eCRF	electronic case report form
FAS	full analysis set
FDA	Food and Drug Administration
ICH	International Conference on Harmonisation
IQ	Interquartile
IWRS	interactive web response system
LLOQ	lower limit of quantification
MedDRA	Medical Dictionary for Regulatory Activities
MRD	minimum required dilution
NAb	neutralizing antibodies
PPI	per protocol immunogenicity analysis set
Pre F	prefusion conformation-stabilized F protein
PT	Preferred term
RSV	respiratory syncytial virus
QTL	Quality Tolerance Limit
SAE	serious adverse event
SAP	Statistical Analysis Plan
SD	standard deviation
SMQs	standardized MedDRA queries
SOC	System organ class
TEAE	treatment-emergent adverse event
VNA	virus neutralization antibody
WHO	World Health Organization

**6.2. Appendix 2 Changes to Protocol-Planned Analyses**

The safety laboratory data are planned to be assessed according to both local laboratory normal ranges as well as FDA toxicities grades.

### 6.3. Appendix 3 Demographics and Baseline Characteristics

The following demographic and baseline characteristics will be summarized. Table 5 presents a list of the demographic variables that will be summarized by cohort and vaccine regimen and overall, for the FAS.

**Table 5 – Demographic Variables**

Continuous Variables:	Summary Type
Age (years)	Descriptive statistics (N, mean, standard deviation [SD], median and range [minimum and maximum], and IQ range).
Weight (kg)	
Height (cm)	
Body Mass Index (BMI) (kg/m  )	
Categorical Variables	
Sex (male, female, undifferentiated)	Frequency distribution with the number and percentage of participants in each category.
Race a (American Indian or Alaska Native, Asian, Black or African American, Native Hawaiian or other Pacific Islander, White, Multiple)	
Ethnicity (Hispanic or Latino, not Hispanic or Latino)	
BMI (<18.5 kg/m  (underweight), 18.5-24.9 kg/m  (Normal or Healthy Weight), 25-29.9 kg/m  (Overweight), ≥30 kg/m  (Obese))	
Risk level of severe RSV disease (Increased risk / Non-increased risk) as collected (CDC definition)	

aIf multiple race categories are indicated, the Race is recorded as 'Multiple'

#### **6.4. Appendix 4 Protocol Deviations**

Major protocol deviations will be summarized.

In general, a list of major protocol deviations that may have the potential to impact participants' rights, safety or well-being, or the integrity and/or result of the clinical study will be specified in a major protocol violation criteria document. Participants with major protocol deviations will be identified prior to database lock and the participants with major protocol deviations will be summarized by category. In addition, minor and major protocol deviations related to COVID-19 will be tabulated.

## 6.5. Appendix 5 Prior and Concomitant Medications

The analysis of concomitant therapies will be done using the WHO drug coded terms. Based on their start and stop date, concomitant therapies will be reported in each applicable phase. If a concomitant therapy record misses components of its start and/or stop dates (time, day and/or month and/or year):

- In case of partial start or stop dates, the concomitant therapy records will be allocated to periods using the available partial information, without imputations. If, for example, only month and year are available, these will be compared to the month and the year of the periods, and the concomitant therapy record will be allocated to the period(s) where these date parts match. This rule may lead to assignment to multiple periods. The same rule applies for identifying whether a concomitant therapy was administered during 8 days following vaccination. If for example, the vaccination was administered on the 30 December 2021 and the concomitant therapy start date is January 2022, then the concomitant therapy will be assumed to have started within 8 days of the vaccination.
- In case of a completely missing start date, the concomitant therapy will be considered as having started before the study.
- In case of a completely missing end date, the concomitant therapy will be considered as ongoing at the end of the trial.

There will be special attention to any systemic use of analgesics/antipyretics, started during 8 days following each vaccination (00:00 of day of vaccination + 7 days). Following ATC/DD codes will be used for this: N02A (OPIOIDS) and N02B (OTHER ANALGESICS AND ANTIPYRETICS), M01A (ANTIINFLAMMATORY AND ANTIRHEUMATIC PRODUCTS, NON-STEROIDS) and M01B (ANTIINFLAMMATORY/ANTIRHEUMATIC AGENTS IN COMBINATION) (ATC/DD Index). The classes will be added in a footnote in all related tables and listings. For the use of analgesics/antipyretics which are taken on the day of vaccination, an exception is made in case the time is before vaccination. In this case, the concomitant medication is also allocated to the Post-dose period. Tables will be created for all concomitant medication and concomitant medications of special interest.

Prior medications will be summarized by cohort and vaccine regimen and overall and ATC term.

